#### **Determination of Sample Size**

##### **Phase Ia**

The number of patients to be enrolled in Phase Ia will depend upon the observed safety and PK/PD profile, which will determine the number of dose escalations.

**Phase IIa**

At the RP2D, a total of approximately 100 patients *have been* enrolled to further assess the safety, tolerability, preliminary evidence of anti-tumor activity, and exploratory PD markers of response of GDC-0810 in 3 distinct patient populations (Cohorts A1 and A2 will be combined for analysis purposes).

**Phase Ib**

Approximately 5 patients *have been* enrolled in the Phase Ib dose escalation cohorts (Cohorts C0 and C1). *No additional patients will be enrolled.*

## LIST OF ABBREVIATIONS

Abbreviation	Definition
21/7	21/7=Days 1–21 of 28-day cycle (no dosing holiday)
28/7	28/0=Days 1–28 of 28-day cycle (no dosing holiday);
AE	adverse event
AI	aromatase inhibitor
ANC	absolute neutrophil count
ASCO	American Society of Clinical Oncology
BID	bis en die (twice daily)
CBC	complete blood count
CBR	clinical benefit rate
CFR	Code of Federal Regulations
CLIA	Clinical Laboratory Improvement Amendments
CRF	case report form
CSF	colony stimulating factors
CTCAE	Common Terminology Criteria for Adverse Events
ctDNA	circulating tumor DNA
DLT	dose-limiting toxicity
eCRF	electronic Case Report Form
ECOG	Eastern Cooperative Oncology Group
ER	estrogen receptor
ESR1	ER- $\alpha$
FDA	U.S. Food and Drug Administration
FES-PET	fluoroestradiol positron emitting tomography
FISH	fluorescence in situ hybridization
FSH	follicle stimulating hormone
GCP	Good Clinical Practice
GFR	glomerular filtration rate
GI	gastrointestinal
GIST	gastrointestinal stromal tumor
HER2	human epidermal growth factor 2
HIPAA	Health Insurance Portability and Accountability Act of 1996
IC 50	50% inhibitory concentration
ICF	Informed Consent Form
ICH	International Conference on Harmonisation
IHC	immunohistochemistry
IMP	investigational medicinal product

Abbreviation	Definition
IRB	Institutional Review Board
IV	intravenous
LBD	ligand-binding domain
LHRH	luteinizing hormone-releasing hormone
LPLV	last patient last visit
mBC	metastatic breast cancer
MTD	maximum tolerated dose
NCI	National Cancer Institute
ORR	objective response rate
PD	pharmacodynamic
PET	positron emitting tomography
PGx	pharmacogenomic
PIK3CA	phosphatidylinositol-4,5-bisphosphate 3-kinase, catalytic subunit alpha
PK	pharmacokinetic
PO	by mouth
QD	once daily
Q4W	every 4 weeks
QTc	corrected QT interval
Rb	retinoblastoma
RECIST	Response Evaluation Criteria in Solid Tumors
RP2D	recommended phase II dose
SAE	serious adverse event
SERD	selective estrogen receptor down-regulator
SHBG	sex hormone-binding globulin
SOC	system organ class
T max	time of maximal plasma concentration
ULN	upper limit of normal
VTE	venous thromboembolism

## 1. BACKGROUND ON ESTROGEN RECEPTOR POSITIVE BREAST CANCER

Breast cancer is the most common form of cancer and the leading cause of cancer death in women worldwide, accounting for more than 1,300,000 new cases and nearly 500,000 cancer deaths annually ([Jemal et al. 2011](#)). Approximately 80% of all breast cancers express and are dependent on the estrogen receptor (ER) for tumor growth and progression. Modulation of estrogen activity and/or synthesis is the mainstay of the therapeutic approach in women with ER-positive (ER+) breast cancer. However, despite the effectiveness of available hormonal therapies such as tamoxifen, aromatase inhibitors (AIs; e.g., anastrozole, letrozole, and exemestane), and full ER antagonists/degraders (e.g., fulvestrant), many patients ultimately relapse or develop resistance to these agents and therefore require further treatment for optimal disease control. As such, there is a need for the development of new ER-targeting therapies with increased anti-tumor activity to further delay disease progression and/or overcome resistance to the currently available hormonal therapies and ultimately prolong survival in women with ER+ advanced breast cancer.

Despite becoming refractory to AIs or tamoxifen, growth and survival of resistant tumor cells remain dependent on ER signaling; therefore, patients with ER+ breast cancer can still respond to second-/third-line hormonal treatment after progression on prior hormonal therapy ([Di Leo et al. 2010](#); [Baselga et al. 2011](#)). Importantly, there is growing evidence that in the endocrine resistant state, ER can signal in a ligand-independent manner ([Miller et al. 2010](#); [Van Tine et al. 2011](#)). An agent with a dual mechanism of action (ER antagonism plus degradation) has the potential to target both ligand-dependent and independent ER signaling and, consequently, improve treatment outcomes in late stage ER+ breast cancer. Furthermore, recent studies have identified mutations in ER- $\alpha$  (ESR1) affecting the ligand-binding domain (LBD) of the ER. Mutant receptors drive ER-dependent transcription and proliferation in the absence of estrogen and reduce the efficacy of ER antagonists, suggesting that LBD-mutant forms of ER are involved in mediating clinical resistance to endocrine therapy and that more potent ER antagonists may be of substantial therapeutic benefit ([Li et al. 2013](#); [Robinson et al. 2013](#); [Toy et al. 2013](#)).

### **Background on GDC-0810**

The term "study drug" will be used throughout the protocol to refer to GDC-0810. GDC-0810 is a novel, potent ER- $\alpha$  antagonist that *was* being developed for use as a single agent or in combination with other anti-cancer therapies as treatment for ER+ advanced breast cancer. *The development of GDC-0810 has been halted as a result of a Sponsor decision to evaluate strategic options for this molecule. The decision to halt the development of GDC-0810 is not due to any safety concerns. No further patients will be enrolled into GDC-0810 studies.*

GDC-0810 is a small-molecule therapeutic agent that competes with estrogens for binding to the ER with low nanomolar potency. *In MCF-7 breast cancer cells, the activity of GDC-0810 differentiates from that of first generation ER antagonists, such as tamoxifen, fully antagonizing the response of ER to estrogens and inducing proteosomal degradation of ER $\alpha$ . In other ER+ breast cancer cell lines, such as HCC1500, MDA-MB-330, and Cama1 cells, GDC-0810 attenuates the transcriptional and proliferative response of ER to estrogens without inducing significant ER $\alpha$  degradation. GDC-0810 has a non-steroidal structure and displays good oral bioavailability in all nonclinical species tested, unlike fulvestrant, which has a steroid structure and exhibits poor bioavailability.*

## **Summary of Nonclinical Data**

GDC-0810 is a potent ER- $\alpha$  antagonist resulting in robust inhibition of ER signaling and inhibition of breast tumor cell proliferation. *In vivo*, GDC-0810 exhibited dose dependent anti-tumor activity in both tamoxifen-sensitive and tamoxifen-resistant MCF7 xenograft models of ER+ breast cancer. In all models, the efficacious dose range was 10–100 mg/kg/day, and all doses were well tolerated. Efficacy in tamoxifen-resistant xenograft models correlated with efficient antagonist activity on ER target genes and reduction of ER- $\alpha$  tumor levels. Fulvestrant appeared to be less efficacious than GDC-0810 in these models.

### **1.1 GDC-0810 SINGLE AGENT CLINICAL SAFETY SUMMARY**

As of 1 October 2014, enrollment in the Phase I dose-escalation portion of the study was completed with 41 patients enrolled at doses from 100 mg to 800 mg.

As of 15 April 2016, one of 6 patients had experienced a dose-limiting toxicity (DLT) of Grade 3 diarrhea in the 800-mg once daily (QD) fasting cohort, which resolved with dose modification and antidiarrheal therapy. A maximum tolerated dose (MTD) was not determined. However, given the high proportion of gastrointestinal (GI) adverse events, doses of 800 mg were deemed intolerable in the clinical setting of breast cancer.

A recommended Phase II dose (RP2D) of 600 mg QD administered under fed conditions (i.e., 30 minutes after eating a meal) was selected based on the overall safety/tolerability and pharmacokinetic (PK) profile of GDC-0810.

As of 15 April 2016, adverse events of any grade related to study drug occurring at >20% frequency in the Phase Ia study were diarrhea (76%), nausea (66%), fatigue (59%), vomiting (34%), decreased appetite (29%), flatulence (27%), abdominal pain (24%), anemia (24%), dyspepsia (24%), hot flushes (24%), hypertriglyceridaemia (24%), muscle spasms (24%), and aspartate aminotransferase increase (22%) (n=41 patients treated at doses from 100 mg to 800 mg). Diarrhea was mostly Grade 1, intermittent in nature, and manageable with dose modifications, dietary adjustments, and treatment with loperamide as needed. As of 15 April 2016, the median treatment duration is 123 days (range 28–790 days) for patients in the Phase Ia study.

As of 9 September 2016, 107 patients have been enrolled in the *combined Phase Ib Cohort D1 and Phase IIa* dose-expansion portion of Study GO29642. *Phase IIa* investigated GDC-0810 at the RP2D of 600 mg QD administered within 30 minutes after a meal. *Phase Ib Cohort D1* investigated 600 mg of GDC-0810 in combination with a luteinizing hormone-releasing hormone (LHRH) agonist. Six patients were enrolled in Cohort D1, thus the 107 patients are predominantly from the *Phase IIa* portion of Study GO29642, Adverse events of any grade related to study drug occurring at >20% frequency in the *Phase IIa* study were diarrhea (44%), nausea (38%), fatigue (36%), and hot flush (21%). Administering GDC-0810 within 30 minutes after a meal may have lowered the incidence of GI toxicities (diarrhea, nausea, vomiting) observed in *Phase IIa*, compared with the *Phase Ib* experience with GI toxicities when GDC-0810 was administered under fasting or non-fasting conditions. Safety data for the *Phase IIa* study remain preliminary with the median treatment duration being 77 days (range 1–547 days).

As of 9 September 2016, 4 patients had been enrolled in the *Phase 1b dose-escalation combination Cohort C1* that examined GDC-0810 at 400 mg in combination with palbociclib at 125 mg. Adverse events of any grade related to study drug occurring at >20% frequency in *Cohort C1* were diarrhea (50%), nausea (75%), fatigue (50%), hot flush (25%), decreased appetite (25%), and gastroesophageal reflux disease (25%). Safety data for *Cohort C1* remain preliminary with a median treatment duration of 134 days (range 56–138 days),

As of 9 September 2016, among potential risks of GDC-0810, regardless of relatedness, no cases of endometrial cancer or phototoxicity were reported in either portion of Study GO29642. Acute renal failure was reported in 2 (1.3%) patients across all phases of Study GO29642 (combined  $n=148$ ), neither case was considered related to GDC-0810. Regardless of relatedness, 9 (6.1%) venous thromboembolic events (VTEs) were reported across all phases of Study GO29642. Adverse event terms were pulmonary embolism and deep vein thrombosis. Grades ranged between 2 and 4. All patients were successfully anti-coagulated following diagnosis of their thromboses. As described in the Investigator's Brochure, Version 4 (January 2017), the only identified risks for GDC-0810 are diarrhea, vomiting, and nausea. For a full discussion of the adverse event profile of GDC-0810, refer to Section 6 of the Investigator's Brochure.

Adverse events observed for GDC-0810 thus far are similar to those that have been observed with other endocrine agents and are amenable to monitoring, are manageable, and are reversible.

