## 1.2 CLINICAL PK SUMMARY

The clinical pharmacokinetics of GDC-0810 is under investigation in the ongoing clinical Phase Ia/Ila Study GO29642. Preliminary PK information from this study is summarized below.

- GDC-0810 was rapidly absorbed with peak concentrations achieved at 1–3 hours after dosing.
- The mean terminal half-life was approximately 8 hours, and mean apparent oral clearance was 8 L/hour after a single dose of GDC-0810 at 600 mg under the non-fasted condition. Consistent with the half-life, minimal drug accumulation was observed following multiple dosing.
- GDC-0810 exposure in the fasted state increased with dose across the entire dose range tested (100–800 mg).
- In the Phase Ia *portion of the study*, at 600 mg QD, mean $\pm$ SD steady state  $AUC_{0-6}$  and  $C_{max}$  for GDC-0810 was  $41.1 \pm 27.5 \mu\text{g} \cdot \text{hour/mL}$  and  $11.8 \pm 6.61 \mu\text{g/mL}$ , respectively, under the fasted state (n=6), and  $74.9 \pm 30.1 \mu\text{g} \cdot \text{hour/mL}$  and  $25 \pm 8.35 \mu\text{g/mL}$ , respectively, under the nonfasted state (n=5).
- In the Phase Ila *portion of the study*, at the RP2D of 600 mg QD under the fed state, mean $\pm$ SD steady state  $AUC_{0-6}$  and  $C_{max}$  for GDC-0810 was  $39.5 \pm 22.5 \mu\text{g} \cdot \text{hour/mL}$  (n=40) and  $14.3 \pm 7.3 \mu\text{g/mL}$  (n=42), respectively.

Based on pharmacodynamic (PD), clinical tolerability, and preliminary PK data collected to date, once-daily administration of 600 mg under fed conditions (within 30 minutes after eating a meal) was selected as the single-agent RP2D for GDC-0810. See the GDC-0810 Investigator Brochure for further details.

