#### **10.1 TREATMENT DOSE ASSIGNMENT**

##### **10.1.1 Phase Ia**

Standard 3+3 design will be followed for dose-escalation in Phase Ia. The starting dose in Phase Ia of GDC-0810 single agent (Cohorts 1–9) will be 100 mg per day, followed by dose escalation to 200 mg (dose level 2), and by 200 mg increments thereafter ([Table 3](#)).

In Phase Ia, a minimum of 3 evaluable patients will be entered at each dose level. If 1 out of the first 3 patients enrolled at any given dose level experiences a DLT, 3 additional patients will be assigned to that dose level. If  $\leq 1$  patient in 6 experiences a DLT, dose escalation will proceed.

In Phase Ia if  $\geq 2$  patients at any given dose level experience a DLT, dose escalation will stop and the MTD may be defined as either the previous dose level or upon further evaluation of an intermediate lower dose level (e.g., by 100 mg decrement).

If no DLTs are observed, the RP2D will be based on the overall safety and PK/PD profile of GDC-0810 single agent (Phase Ia), and not necessarily the MTD. The decision to dose escalate or dose reduce will be made during dose escalation data review teleconferences held between the Sponsor and the investigators.

If only 3 patients have been treated at a dose level under consideration as the MTD and/or RP2D, a minimum of 3 additional patients will be treated at that dose level to confirm the MTD and/or RP2D.

In Phase Ia, dose escalation will continue until either of the following has been observed:

The MTD has been exceeded (incidence of DLT  $\geq 33\%$ ); or

Pharmacokinetic futility (defined as a lack of increase in exposure with increasing doses of GDC-0810 in at least two successive dose levels) is encountered.

Patients enrolled in Phase Ia will continue treatment at their assigned dose level for at least 2 cycles and observed for cumulative toxicity. After 2 cycles, they may then be treated at the next higher dose level provided it has been shown to be safe (passed the DLT evaluation period) in a previously treated cohort at the discretion of the investigator and in agreement with the patient.

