### **10.1.3 Phase Ib**

#### **10.1.3.1 Cohort C1**

*GO29642 study enrollment in Phase Ib has been discontinued. No patients will be enrolled in Phase Ib Cohorts C2 and C3.*

Standard 3+3 design will be followed for dose-escalation in Cohort C1 of the Phase Ib study.

The starting dose for Phase Ib Cohort C1 dose escalation of GDC-0810 will be 400 mg per day on Days 1–28 of a 28-day schedule, taken together with 125 mg palbociclib administered on Days 1–21 of a 28-day schedule (21/7) ([Table 2](#)).

In Cohort C1 of Phase Ib, a minimum of 3 evaluable patients will be entered at each dose level. If 1 out of the first 3 patients enrolled at any given dose level experiences a DLT, 3 additional patients will be assigned to that dose level. If  $\leq 1$  patient in 6 experiences a DLT, dose escalation will proceed. If dose level C1 is deemed intolerable in the absence of DLTs, de-escalation to dose level C0 may occur.

In Cohort C1 of Phase Ib, if  $\geq 2$  patients at any given dose level experience a DLT, dose escalation will stop and the MTD may be defined as either the previous dose level or upon further evaluation of an intermediate lower dose level.

In addition to any DLTs, other available relevant demographic, adverse event, laboratory, dose administration, PK, and PD data will be reviewed prior to all dose escalation decisions.

If no DLTs are observed, the RP2D will be based on the overall safety and PK/PD profile of GDC-0810 and palbociclib, and not necessarily the MTD. The decision to escalate or reduce the dose will be made during dose-escalation data review teleconferences held between the Sponsor and the investigators.

If only 3 patients have been treated at a dose level under consideration as the MTD and/or RP2D, a minimum of 3 additional patients will be treated at that dose level to confirm the MTD and/or RP2D.

Patients enrolled in Cohort C1 of Phase Ib will continue treatment at their assigned dose level for at least 2 cycles and observed for cumulative toxicity. After 2 cycles, they may then be treated at the next higher dose level provided it has been shown to be safe (passed the DLT evaluation period) in a previously treated cohort at the discretion of the investigator and in agreement with the patient.

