### **15.2.3 Phase Ib**

Approximately 5 patients *have been* enrolled in the Phase Ib dose escalation cohorts (Cohorts C0 and C1). *No additional patients will be enrolled.*

Because the dose escalation portion of Phase Ib follows the same dose escalation rules as the Phase Ia, the probability of escalation from dose level C1 to dose level C2 is also shown in [Table 11](#). Similarly, the probability of failing to observe toxicity in dose

escalation cohorts (Cohorts C0 and C1) and safety run-in cohort (Cohort D1) is shown in [Table 14](#).

Approximately 4 patients *have been* enrolled at the RP2D of GDC-0810 and palbociclib, and approximately 6 patients *have been* enrolled at 600 mg of GDC-0810 and an LHRH agonist. With 10 patients, there is a 80% probability of observing an adverse event with a true underlying probability of 15%.

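### Section 10.1.1 still lets a Phase Ia patient move up to 800 mg once daily fasting, a dose that Section 1.1 records as intolerable

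*Combined protocol and SAP*

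**What the plan says.** Section 1.1 gives the Phase Ia outcome. At the top dose, "one of 6 patients had experienced a dose-limiting toxicity (DLT) of Grade 3 diarrhea in the 800-mg once daily (QD) fasting cohort". No MTD was determined. On the strength of the gastrointestinal events, not the DLT count, the section then concludes that "doses of 800 mg were deemed intolerable in the clinical setting of breast cancer", and it names 600 mg once daily with food as the RP2D.

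Section 10.1.1 gives the Phase Ia dose rules. If no more than one "patient in 6 experiences a DLT, dose escalation will proceed". Later in the section, patients stay at their assigned level for at least two cycles. They may then be treated at the next higher level "provided it has been shown to be safe (passed the DLT evaluation period) in a previously treated cohort", at the investigator's discretion and with the patient's agreement. Table 3 sets steps of 200 mg above 400 mg and states no ceiling.

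The Version 9 amendment rationale and Section 7 close enrollment but let Phase Ia patients with clinical benefit stay on treatment.

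**The concern.** The bracket in Section 10.1.1 reduces safety to one test, passing the DLT period. Section 1.1 rejected 800 mg on a different ground, which that test does not capture. A dose can therefore be intolerable in one section and eligible for an individual patient's dose increase in the other.

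The rule is not purely historical. Closing enrollment ends the opening of new cohorts, but it does not switch off a permission that applies to patients already on treatment. An investigator who applies Section 10.1.1 to the letter could move a continuing patient to a dose that the same protocol calls intolerable, without departing from Section 10.1.1.

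**Working it through.** **Inputs.**
- DLTs at 800 mg once daily fasting: 1 of 6 (Section 1.1).
- Rule for passing a level: at most 1 DLT in 6 (Section 10.1.1).
- Limit for having exceeded the MTD: DLT incidence of 33% or more (Section 10.1.1).
- Dose levels: 100, 200 and 400 mg, then steps of 200 mg (Table 3).

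**The plan's own figure.** Table 11 is the 3+3 rule computed from DLTs alone:

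P(escalate) = (1−p)³ + 3p(1−p)² × (1−p)³

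At p = 0.10 this is 0.729 + 0.243 × 0.729 = 0.906, against 91% in the table. From p = 0.05 to 0.90 the formula gives 97.3, 90.6, 70.9, 49.4, 30.9, 17.2, 8.2, 3.2, 0.9 and 0.1%. Every entry reproduces. The formula counts 1 DLT in 6, reached as 1 of 3 then 0 of 3, as a pass.

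**Does 800 mg pass the test in the bracket?**
- Observed incidence: 1/6 = 16.7%, below 33%. A second DLT would have given 2/6 = 33.3% and reached the limit.
- So the 800 mg once-daily fasting cohort passed.

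**Is 800 mg the next level above 600 mg?**
- 400 + 200 = 600, and 600 + 200 = 800. Yes.

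**Is it excluded elsewhere?**
- Section 10.1.1 does not name 800 mg and sets no cap on individual increases.
- The list of permitted doses in Section 10.4.1 (600, 400 and 200 mg) is written for Phase IIa.

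**How much does a pass show?** The exact 95% confidence interval for 1/6 runs from 0.4% to 64.1%. At a true DLT rate of 1/3 the formula gives 0.2963 + 0.4444 × 0.2963 = 0.428, so such a dose would still pass about 43% of the time. A pass says little about the DLT rate, and it does not measure the lower-grade gastrointestinal burden at all.

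**Side by side.** For a Phase Ia patient on 600 mg once daily fasting who has completed two cycles, Section 10.1.1 says that 800 mg is open and Section 1.1 says that 800 mg is intolerable.

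**The case against.** The strongest reply is that the permission is narrow. It is optional, it needs clinical judgement and the patient's consent, and the investigator has Section 1.1 in the same document. The 1 of 6 result belongs to once-daily fasting dosing. Phase Ia also tested 600 mg without fasting and twice-daily regimens, and the documents give no DLT result for 800 mg once daily with food. Nothing shows that a patient on 600 mg remains in Phase Ia. All of this stands and lowers the weight of the point, but none of it makes the two sections agree.

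Three stronger readings are tempting, and the documents do not support them.

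- *A reader might infer that the RP2D was chosen on a ground absent from the design.* Section 7.1 makes escalation depend on tolerability as well as safety. Section 15.2.1 ties the number of escalations to the observed safety and PK/PD profile. Section 10.1.1 gives the decision to the sponsor and investigators in teleconference. The objective is an MTD and/or an RP2D, and Section 1.1 already reports that no MTD was found. The clause in Section 10.1.1 that bases the RP2D on the overall profile is conditional on there being no DLTs, so it does not literally apply, but the other passages do not depend on it.
- *A reader might infer that escalation beyond 800 mg is still directed.* The section says "In Phase Ia, dose escalation will continue until either of the following has been observed", and neither criterion was met: incidence was 16.7%, and Section 1.2 says that "exposure in the fasted state increased with dose across the entire dose range tested". But Phase Ia escalation enrollment was complete by 1 October 2014 and all enrollment is now closed, so no further cohort can open.
- *A reader might infer that Table 11 and its reuse for Phase Ib are wrong.* Section 10.1.3.1 adds "If dose level C1 is deemed intolerable in the absence of DLTs, de-escalation to dose level C0 may occur", while Section 15.2.3 says that "the dose escalation portion of Phase Ib follows the same dose escalation rules as the Phase Ia". The table is correct and is labelled by true DLT rate, the DLT rules in the two sections are nearly identical, and the added clause concerns optional de-escalation to C0. The table's stated Phase Ib use is the step from C1 to C2, and C2 will not enroll.

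**Conclusion.** The inconsistency holds, and it is minor. It concerns one bracketed phrase in Section 10.1.1, which classes 800 mg once daily fasting as safe on 1 DLT in 6 (16.7% against a 33% limit) while Section 1.1 calls the dose intolerable.

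The conclusion rests on two readings: that the bracket defines what safe means in that sentence, and that the sentence still governs Phase Ia patients who continue under Version 9. It has practical effect only if such a patient, on the level below 800 mg, is still being treated; the documents do not settle that. It does not extend to 800 mg with food or to twice-daily dosing, and it does not question the choice of RP2D, the conduct of the escalation or Table 11.

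**What to change.** Reconcile Sections 1.1 and 10.1.1. Reword the bracketed phrase in Section 10.1.1 so that it and the Section 1.1 decision give one answer on whether an individual Phase Ia patient may be moved to 800 mg. Which answer is right is for the sponsor to decide.

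The cost is one phrase in a protocol that is already being amended to Version 9 standard text. No patients, procedures or analyses are added, and Table 11, Section 15.2.3 and the reported Phase Ia result need no change on this account.
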